9.1.3 Methods for Evaluation of Measurable Disease

All measurements should be taken and recorded in metric notation using a ruler or calipers. All baseline evaluations should be performed as closely as possible to the beginning of treatment and never more than 4 weeks before the beginning of the treatment.

The same method of assessment and the same technique should be used to characterize each identified and reported lesion at baseline and during follow-up. Imaging-based evaluation is preferred to evaluation by clinical examination when both methods have been used to assess the antitumor effect of a treatment.

Conventional CT, FDG-PET/CT, and MRI These techniques should be performed with cuts of 10 mm or less in slice thickness contiguously. Spiral CT should be performed using a 5 mm contiguous reconstruction algorithm. This applies to tumors of the chest, abdomen, and pelvis. Head and neck tumors and those of extremities usually require specific protocols.

9.1.4 Response Criteria

9.1.4.1 Response Assessment of Bone Metastases

Radiographic assessment of bone metastasis can be difficult as remodeling bone may lead to residual abnormalities on bone scan, CT scan, and MRI scan. This leads to inherent difficulties in using RECIST 1.1 criteria for response assessment. For the purposes of the current protocol, response at bone metastasis will be graded as follows:

Complete response (CR) = A negative FDG-PET at the irradiated lesion in patients who have a positive FDG-PET at the time of SBRT at the target lesion. FDG-PET is optional on study. Therefore, CR will be recorded but not required to constitute a response.

Progressive disease (PD) = Any of the following will constitute PD:

- Development of a new soft tissue mass ≥ 1 cm in maximum axial dimension at a previous site of bone metastasis without a soft tissue component or with a soft tissue component < 1 cm in maximum axial dimension on previous evaluations.
- For bone metastasis with a soft tissue component ≥ 1 cm in maximum axial dimension on previous evaluations, an increase in the longest axial diameter of the soft tissue component by $> 20\%$.
- A previous bone metastasis that was positive on FDG-PET, became negative with protocol therapy, and then becomes positive again should prompt concern

for progression at that site. Confirmatory testing is required to document progression at a previous site of bone metastasis. Together with return of FDG-PET uptake, MRI scan with documentation of an enhancing bone lesion will constitute adequate evidence to support progression at that site. Biopsy is strongly encouraged, but not required to confirm progression at a previous site of bone metastasis.

- Biopsy evidence of viable sarcoma at a previously radiated bone metastasis.

Stable disease (SD) = Patients not meeting either CR or PD criteria.

9.1.4.2 Evaluation of Best Overall Response

The best overall response is the best response recorded from the start of the treatment until disease progression/recurrence (taking as reference for progressive disease the smallest measurements recorded since the treatment started). Best overall response will be based on the overall response of the target lesions.

9.1.5 Duration of Response

Duration of overall response: The duration of overall response is measured from the start of the treatment until the criteria for progression are met, taking as reference the smallest measurements recorded since the treatment started.

9.1.6 Clinical Response Parameters

Progression-free survival (PFS) is defined is the time from starting treatment to the time of first documented tumor progression or death due to any cause, whichever occurs first. Death is considered as an event here. For subjects whose disease does not progress or who do not die, PFS will be censored at the time of the last visit.

Time to progression (TTP) is defined as the time from starting treatment to the time of first documented tumor progression. Subjects who do not progress will be censored at the time of the last contact. In addition, death from any cause will also be censored.

Overall survival (OS) is defined as the time from starting treatment until death due to any cause. For subjects who do not die, time to death will be censored at the time of last contact.

Local Control (LC) is defined as the time from starting treatment until local relapse is documented. The target lesion will be considered locally controlled if criteria for progression are not met, taking as reference the smallest measurements recorded since the treatment started.

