5.6.2 At 3, 6, 9, 12, 18, 24, 30, and 36 months Post-SBRT

5.7 Duration of Follow-Up

It is anticipated the patients that remain on-study will be followed for 3 years.

Patients will remain enrolled on this protocol until there is evidence that their disease has progressed either locally or distally, at which case they will be removed from the protocol and be followed for survival only. Patients removed from study for unacceptable adverse events will be followed per protocol until resolution or stabilization of the adverse event and then followed for survival only.

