5.8 Criteria for Removal from Study

Patients will be removed from study when any of the criteria listed in Section 5.5 applies. The reason for study removal and the date the patient was removed must be documented in the Case Report Form.

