13.3 Analysis of Secondary Endpoints

13.3.1 Definition of secondary outcomes/endpoints:

- To describe the toxicity of SBRT delivered to a dose of 4000 cGy in 5 fractions of 800 cGy each for the population enrolled using grading with CTCAE v. 4.0
- The clinical response rate of each lesion will be assessed by serial CT assessment (FDG-PET/CT is optional for assessment) and defined by criteria as defined above. The absence of progression will constitute a response. Therefore, lesionspecific CR or SD will be measured as a response.
- To assess long-term clinical outcomes of this patient population after completion of SBRT by measuring relapse-free survival and overall survival. Relapse-free survival will be measured from time of enrollment to date of disease progression or death. Patients who are lost to follow-up will be censored for determination of

progression-free survival on the date of their last evaluation. Overall survival is defined as time from enrollment to death due to any cause.

- To assess quality of life following completion of SBRT using pre- and post-SBRT completion of the Brief Pain Inventory form and 10 point Visual Analog Scale which will be filled out by the patient at the treatment response intervals outlined above.

13.3.2 Analysis plan for secondary endpoints:

- Toxicities will be graded and tabulated at the time of each follow-up assessment. The proportion of toxicities by type and grade will be reported with exact 95% confidence intervals.
- Each metastatic lesion will be considered a target lesion and independently evaluated for response. The proportion of these lesions that have a stable or better response and the intra-cluster correlation will be estimated with an intercept only generalized estimating equation (GEE) regression. This will be estimated directly with SAS Genmod by specifying binomial variation, the identity link function, and an exchangeable correlation structure.
- Hazard rate estimates and 95% confidence intervals as well as Kaplan-Meier (KM) estimates will be used to summarize survival (OS), progression free survival (PFS), time to progression (TTP) and locoregional control (LRC) functions over time. The median OS, PFS, TTP and LRC will be reported. Cox proportional hazards models will be used to evaluate the impact of key covariates on these endpoints as the sample size permits.

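### Time to progression is censored at last contact, so time without scans in survival-only follow-up counts as progression-free and the TTP curve is biased long

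*Combined protocol and SAP*

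**What the plan says.** Section 9.1.6 censors TTP in patients without progression as follows: "Subjects who do not progress will be censored at the time of the last contact". It adds: "In addition, death from any cause will also be censored". Overall survival in the same section is also censored at last contact. For progression-free survival (PFS), section 9.1.6 says that "PFS will be censored at the time of the last visit", while section 13.3.1 censors patients lost to follow-up for "progression-free survival on the date of their last evaluation".

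Section 5.7 describes two routes into survival-only follow-up. Patients who progress enter it: "at which case they will be removed from the protocol and be followed for survival only". Patients removed for unacceptable adverse events are followed per protocol "until resolution or stabilization of the adverse event and then followed for survival only", and progression is not a condition. Section 5.8 widens removal: "Patients will be removed from study when any of the criteria listed in Section 5.5 applies". It does not say what follow-up comes after removal on the other section 5.5 criteria.

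Section 13.3.2 reports hazard rates, Kaplan-Meier curves and medians for TTP and PFS.

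**The concern.** TTP needs a documented progression. A patient with no scheduled scans has little chance of one, yet a later survival contact keeps that patient at risk up to the date of the contact. Take a patient who leaves imaging unprogressed at month 2 and is alive at a month-36 contact. TTP credits that patient with 34 progression-free months that nobody checked. The error runs in one direction: the curve and median are too long and the hazard too low. TTP and PFS can then differ for a reason that has nothing to do with deaths. The PFS date itself depends on which section the analyst follows.

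**Working it through.** The documents give no TTP event count, median or dropout fraction, so there is no stated figure to reproduce. The first step is a reading of the text; the rest is illustration.

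**1. Who is exposed.**
- Patients in survival-only follow-up after progression already have their TTP event, so censoring does not apply to them.
- Patients removed for adverse events without progression are exposed once the event resolves or stabilizes.
- Patients removed on other section 5.5 criteria are exposed only if they stay in contact, which the plan leaves open.
- Section 5.7 says "It is anticipated the patients that remain on-study will be followed for 3 years". Progression-free patients contacted after month 36 could be exposed, but those contacts cannot change estimates at 12 or 24 months.

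**2. Illustration: inputs, all assumed.** Exponential progression with median 9 months, λ = ln 2/9 = 0.0770 per month. Exponential death with median 24 months, μ = ln 2/24 = 0.0289 per month, independent of progression. A fraction q is assigned to leave imaging at a time L uniform on months 1-6. Contact continues to death or month 36. No progression is documented after L, and progression before L is dated exactly.

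**3. Truth.** S(t) = 2^(−t/9). S(12) = 0.397 and S(24) = 0.157.

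**4. Estimate with censoring at last contact.** For t > 6, the Kaplan-Meier curve tends to (1 − q)·S(t) + q·a. Here a is the mean of S(L): a = (e^(−λ) − e^(−6λ))/(5λ) = (0.9259 − 0.6300)/0.3851 = 0.768.
- q = 5%: 0.95 × 0.397 + 0.05 × 0.768 = 0.415 at 12 months; 0.95 × 0.157 + 0.05 × 0.768 = 0.188 at 24 months.
- q = 10%: 0.434 and 0.219.
- q = 20%: 0.471 and 0.280.

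Simulation under the same assumptions agrees with these values to within about 0.1 point. At q = 0 there is no bias.

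**5. Median.** Setting the expression in step 4 to 0.5 gives t = −ln[(0.5 − 0.768q)/(1 − q)]/λ, which is 9.4, 9.8 and 10.9 months for the three values of q, against a true 9.

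**6. How many actually leave unprogressed.** Some of those assigned progress or die first. With k = λ + μ = 0.1059, the share that leaves alive and unprogressed is (e^(−k) − e^(−6k))/(5k) = (0.8995 − 0.5297)/0.5295 = 0.698. So q = 5%, 10% and 20% correspond to about 3.5%, 7% and 14% of patients.

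**7. Second model.** Progression is detected only at the month 3, 6, 9, 12, 18, 24, 30 and 36 scans. A fraction f moves to survival-only follow-up after the month-3 scan and stays in contact to month 36, and no deaths are modelled. With an assumed 12-month median, the 24-month estimate is 28.0%, 31.0% and 36.8% for f = 5%, 10% and 20%, against 25.0% with censoring at last scan. Across assumed medians of 9 to 18 months, the 24-month bias is about 2.5 to 13 points.

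**8. PFS.** The study calendar marks a CT at every visit from month 3, so last visit and last scan will usually coincide. The 4-week visit has none. A death in survival-only follow-up is a PFS event. What remains is that sections 9.1.6 and 13.3.1 name different dates.

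**The case against.** The exposed group is narrow. Most patients enter survival-only follow-up because they progressed, and the only route expressly stated for unprogressed patients is removal for an unacceptable adverse event. The section 5.5 criteria are framed as reasons to end a treatment of at most two weeks. The fractions above are assumed: 5% of 20 patients is one patient, and the resulting shift of 2 to 3 points is small beside a sampling standard deviation of about 12 points at 12 months and 11 at 24. If half of the later progressions were documented by other means, the bias would roughly halve; at q = 20% the estimates would be about 43/22% instead of 47/28%. TTP is not named among the objectives in section 1.2 and carries no test or threshold. All of this stands, and it limits the weight of the point. It does not remove it, because the rule as written is wrong for these patients and nothing else in the plan corrects it.

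Censoring at last scan is not a complete remedy either. It recovers the truth only if leaving imaging is unrelated to the risk of progression. With q = 30% and a doubled progression hazard in those assigned to leave, it gives 0.367 at 12 months against a true 0.7 × 0.397 + 0.3 × 0.397² = 0.325.

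A reader might infer that PFS is biased in the same way. The documents do not support that: survival contacts are not called visits, scheduled visits from month 3 carry a CT, and section 13.3.1 already uses last evaluation for patients lost to follow-up. A reader might also infer that the local control curve is wrong. No censoring date is stated for it, which is a gap and not a demonstrated error.

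**Conclusion.** The point holds for TTP. Followed as written, the last-contact rule counts time without scans as progression-free and lengthens the TTP curve and median. The size depends on a fraction the documents do not give. Under the step 2 assumptions, the upward bias is about 2 to 7 points at 12 months and 3 to 12 points at 24 months for 5% to 20% assigned to leave imaging, and zero if none leave. For PFS the finding is a conflict of wording between sections 9.1.6 and 13.3.1, with no bias shown. The primary analysis in section 13.2 counts patients with local control at 6 months and does not use this rule. This is a minor correction to a descriptive secondary analysis.

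**What to change.** In sections 9.1.6 and 13.3.1, state one rule: patients without an event are censored for TTP, PFS and relapse-free survival at the date of the last tumor assessment adequate to judge progression. Keep last contact for overall survival only. Use the same assessment date for the local control curve, which has no stated censoring date. When reporting, give the number of patients who left imaging without progression and the reason, since the rule assumes that leaving is unrelated to progression risk.

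The cost is about one sentence in each section. The dates should already be available from the Response Assessment Form in section 10.1, so no new visits, scans or patients are needed. The downside is slightly shorter follow-up for TTP and PFS.

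### Time to progression censors deaths, and locoregional control has no rule for death or distant progression; the planned Kaplan-Meier summaries overstate failure if read as the proportion of patients failing

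*Combined protocol and SAP*

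**What the plan says.** Section 9.1.6 defines the time-to-event measures. TTP runs from the start of treatment to first documented progression, and of deaths it says: "In addition, death from any cause will also be censored". Progression-free survival (PFS) is handled the other way: "Death is considered as an event here". The third definition is: "Local Control (LC) is defined as the time from starting treatment until local relapse is documented". It gives no censoring rule, and does not mention death or distant progression.

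Section 13.3.2 applies hazard rates and Kaplan-Meier estimates to overall survival (OS), PFS, "time to progression (TTP) and locoregional control (LRC) functions over time". It adds: "The median OS, PFS, TTP and LRC will be reported". The term locoregional control appears only there and is not defined. No cumulative incidence or other competing-risk method is named anywhere in the document.

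Section 5.7 sets the follow-up: "It is anticipated the patients that remain on-study will be followed for 3 years". It also treats local and distant progression alike. Once either is found, patients leave active follow-up, "at which case they will be removed from the protocol and be followed for survival only".

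The primary endpoint in 13.2 is separate: a 6-month proportion with an exact binomial 90% interval.

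**The concern.** A patient who dies without progression cannot progress later. Kaplan-Meier with that death censored treats the patient as still able to fail, at the same rate as those under observation. Its complement therefore describes a setting in which nobody dies, and it cannot be lower than the proportion of patients who actually fail.

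Local control has a second such event. Under 5.7, a patient who progresses elsewhere goes to survival follow-up only, so protocol assessment of the treated site stops while the patient is alive. The plan does not say whether that time is censored, counted as competing, or followed through to death.

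At stake are the longer-term curves and any medians taken from them. With 36 months of follow-up and the event rules unstated, two analysts could follow 13.3.2 and report quite different local failure figures from the same 20 patients.

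**Working it through.** **The plan's own figures.** It gives none for TTP or LRC. The primary design figures reproduce and use no Kaplan-Meier estimate. The chance of 4 or fewer responders in 6 is 1 - (6 x 0.7^5 x 0.3 + 0.7^6) = 58.0% at a true rate of 70%, and 11.4% at 90% (stated: 58% and 11%). The exact 90% interval for 18/20 is 0.717 to 0.982 (stated: 0.72 to 0.98).

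**Inputs from the document.** Control at 6 months: 90% anticipated, 70% historical (13.2). Follow-up: 36 months (5.7).

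**Assumptions.** Hazards are constant and independent. Mortality is not given, so a range is used: median time to death without local failure of 9 to 36 months. It is called median survival below.

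**Formulas.** With failure rate h and competing rate d per month:
- 1-KM(t) = 1 - exp(-h t)
- cumulative incidence CI(t) = h/(h+d) x [1 - exp(-(h+d) t)]

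**Local failure at 90% control.** h = -ln(0.9)/6 = 0.01756 and d = ln 2 / median survival. 1-KM is 10.0% at 6 months, 19.0% at 12 and 46.9% at 36.

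| Median survival (months) | d | CI at 6 mo | CI at 12 mo | CI at 36 mo | Excess of 1-KM at 36 mo |
|---|---|---|---|---|---|
| 9 | 0.0770 | 8.0% | 12.6% | 18.0% | 28.9 points |
| 12 | 0.0578 | 8.5% | 13.9% | 21.8% | 25.1 |
| 18 | 0.0385 | 8.9% | 15.3% | 27.2% | 19.7 |
| 24 | 0.0289 | 9.2% | 16.2% | 30.7% | 16.2 |
| 36 | 0.0193 | 9.5% | 17.0% | 35.0% | 11.9 |

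The Kaplan-Meier median is ln 2 / 0.01756 = 39.5 months, beyond follow-up. Cumulative incidence never reaches 50% in any row. Neither method gives a median by 36 months.

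**Sensitivity at 70% control.** h = -ln(0.7)/6 = 0.05945. At 36 months 1-KM is 88.2%, against 43.2% to 71.1%. The Kaplan-Meier median is 11.7 months. Cumulative incidence reaches 50% at 13.8 months (median survival 36) to 36.3 months (median survival 12), and never at median survival 9.

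**TTP.** Only deaths without documented progression compete. Let s be their share of first events, so d = h s/(1-s), with h = ln 2 / median TTP and an assumed median TTP of 6 to 12 months.

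| Median TTP by Kaplan-Meier (months) | s | 1-KM at 36 mo | CI at 36 mo | Excess | Month CI reaches 50% |
|---|---|---|---|---|---|
| 6 | 2% | 98.4% | 96.6% | 1.8 points | 6.1 |
| 6 | 10% | 98.4% | 89.1% | 9.3 | 6.3 |
| 6 | 20% | 98.4% | 79.6% | 18.8 | 6.8 |
| 12 | 2% | 87.5% | 86.3% | 1.2 | 12.1 |
| 12 | 10% | 87.5% | 81.1% | 6.4 | 12.6 |
| 12 | 20% | 87.5% | 74.1% | 13.4 | 13.6 |

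**Distant progression.** Take h = 0.01756 and assume a median of 6 months to the end of local assessment, a rate of ln 2/6 = 0.1155. Local failure observed by 36 months is 0.01756/0.1331 x [1 - exp(-0.1331 x 36)] = 13%. With death as the only competing event and median survival 18 months, the table gives 27%. The 13% measures local failure as first event; the 27% measures local failure at any time before death. The plan does not say which it wants.

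**The case against.** Censoring deaths is a recognised definition of TTP, and it is right for cause-specific hazards and Cox models. If 1-KM is meant as the hypothetical no-death quantity, it is not wrong by definition. PFS and OS, which count deaths, are reported alongside. All this stands. But the plan does not label the curves as hypothetical, and that reading needs death to be independent of progression; if it is not, the bias could go either way.

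Some stronger readings are tempting, and the document does not support them:
- A reader might infer that deaths are explicitly censored for LRC as well. The sentence sits in the TTP definition only. For local control the finding is an omission, from which Kaplan-Meier implies censoring.
- A reader might infer that mortality is known to be high, so the overstatement has a fixed size. No mortality rate or median survival is given. Entry requires a minimum life expectancy of 9 months. The protocol summary describes patients beyond cure by existing systemic treatment, yet it and section 2.3 also call patients with limited metastases potentially curable.
- A reader might infer that the promised medians will be wrong. At the anticipated 90% control no local median is reached by 36 months on either method. For TTP the median moves 0.1-0.6 months when 2-10% of first events are deaths without progression, and 0.8-1.6 months at 20%. A large discrepancy appears only for local failure near the 70% historical reference.
- A reader might infer that making death the only competing event is enough. Because of 5.7, carrying patients to death would count unobserved local failures after distant progression as deaths without failure, turning an overstatement into an understatement.

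**Conclusion.** The point holds in limited form. TTP is summarised by Kaplan-Meier with deaths explicitly censored. LRC is summarised the same way without a definition and without a rule for death or distant progression. Read as the proportion of patients failing, 1-KM cannot be too low; that direction needs no mortality assumption.

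The size does. Under constant independent hazards and 90% control at 6 months, the 36-month excess for local failure is about 12-29 points across median survival of 36 down to 9 months. For TTP it is about 1-9 points if deaths without progression are 2-10% of first events, and 13-19 points at 20%. At 6 months the local gap is at most 2 points (10.0% against 8.0-9.5%).

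These are descriptive secondary summaries in 20 patients. The primary analysis, two-stage rule and sample size are untouched. The change should be made, but nothing in the design depends on it.

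**What to change.** In 13.3.2:
- Define LRC as the local control endpoint of 9.1.6, or use that term throughout.
- Report TTP by cumulative incidence (Aalen-Johansen), with death without progression as a competing event.
- Report local control by cumulative incidence, with death and any distant progression that ends local imaging as competing events. Label it local failure as first event, so that it is not read as all local failure before death.
- Drop the Kaplan-Meier medians for TTP and LRC. Give a time to 50% cumulative incidence only if it is reached within follow-up.
- Keep Kaplan-Meier for OS and PFS, and Cox models for TTP and LRC described as cause-specific.

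The cost is SAP wording, with no extra patients or visits. The downside is less direct comparison with older Kaplan-Meier series; a supplementary 1-KM curve, labelled with its censoring rules, can cover that. Local failure after distant progression will remain unmeasured, because the present follow-up does not collect it, and the report should say so.
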